BCG intravesical therapy is a form of immunotherapy commonly used to prevent the recurrence of noninvasive bladder cancer, which occurs in approximately 50-80% of bladder cancer patients within 5 years. 10-20% of all superficial bladder cancer patients will progress beyond superficial recurrence within 5 years. Smoking, poor diets, and large body weights are all potential risk factors for recurrence, but there is also a high propensity for bladder cancer recurrence in general due to its aggressive nature. As treatment, BCG intravesical therapy is instilled in the bladder using a urinary catheter. The intravesical therapy remains in the bladder for about two hours until the patient urinates. The treatment is usually once a week for six weeks and then repeated every 3-6 months for two years. However, intravesical therapy typically causes urinary tract symptoms, such as pain, frequency, burning, inflammation, and bleeding in patients. Symptoms may occur after the very first treatment or become worse over time as therapy continues. As a result, the dose of therapy is often reduced so that symptoms can be treated symptomatically with antibiotics or pain medication. Dose reduction is generally done in 50% increments, and the decision to reduce the treatment dosage is often subjective based on each patient's perception of symptoms.

The isoflavone genistein (4,7,4'-trihydroxyisoflavone) is a phytoestrogen found in high levels in soy products and can be taken as a nutritional supplement for its antioxidant benefits and its estrogenic properties. The genistein supplement is sold over the counter and has less soy isoflavone than commonly found in many healthy diets. For comparison, an 8 ounce glass of soy milk has 15 mg of genistein. Studies have used up to 300 mg of genistein supplement daily, and it has been shown as safe, well accepted, and well tolerated with no known significant toxicities.

Recent epidemiologic reports show that some Asian countries with high soy consumption have a smaller incidence of prostate carcinoma and studies suggest it might be due to the anticancer effects of soy. A study of 41 subjects in 2003 showed that there was a significant slow in the rate of PSA rise in prostate cancer patients after taking 100 mg of genistein supplement daily for 6 monthsⁱ A recent study of 52 subjects in 2010 showed that the short-

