4.2 Secondary objective

- a) A secondary study endpoint will be the presence of cancer and the rate of recurrence as determined by the 10-week biopsy or subsequent standard follow-up visits.
- b) A second secondary study endpoint will be the total dose of intravesical therapy administered over the 6 weeks of treatment. If subjects develop fewer urinary tract symptoms as a result of the genistein supplement, then hypothetically, intravesical therapy dosing would not have to be reduced as much. This will be measured by looking at the level of dose reduction for each treatment week and comparing it across the two arms.

5. Study Design and Methods:

At the pre-operative office visit before intravesical therapy, eligible patients will be screened and enrolled into the study by going through the consent process and signing the consent and HIPAA forms. Each patient will need to report all other medications so that the study team can assess whether certain medications might affect trial outcome.

Patients will be randomized into Arm 1 (placebo) or Arm 2 (genistein supplement) at a ratio of 1:1 stratified by one dichotomized prognostic factor, age. The dichotomization will take place based on whether they are age 60 and above or whether they are age 59 and below. This will allow for similar age groups to be placed in each arm, so that the degree of urinary symptoms while receiving treatment is not skewed depending on the patient's age.

Patients are treated with intravesical therapy once a week for 6 weeks and then return to the office approximately four weeks later for a post-operative visit and biopsy, as is standard care. Study subjects will take their genistein or placebo tablets for a total of 10 weeks, which includes the length of their treatment, as well as the 4 weeks before the post-op visit. Each patient will fill out an International Prostate Symptom Score (IPSS) questionnaire at their baseline office visit when consented. Patients will fill out an IPSS questionnaire at each subsequent intravesical therapy session and their final one-month follow-up appointment (at 10 weeks) either in person or via phone call with a study team member. The IPSS questionnaire will gauge their urinary symptoms throughout their therapy and provide measurable symptom scores for the two arms. The biopsy at 10 weeks, as well as standard 3 months follow-up appointments, is standard care for superficial bladder patients and will help determine cancer rate of recurrence.

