8.1 Power analysis

We hypothesize that, at 6 weeks, the symptom score will increase by 6 (SD = 3.5) relative to the baseline in the placebo arm, while it will only increase by 3 (SD = 3.5) in the synthetic genistein supplement arm. A sample size of 20 patients in each arm can reach 83% power to detect the hypothesized difference at the significance level of 0.05 by one-sided Mann-Whitney test.

In an effort to reach a sample size of 20 patients on each arm, we also hypothesize that there will be a 10% drop-out or non-compliance rate. We will accrue 44 patients, 22 subjects on each arm, for this study with the expectation that 10% will drop out. With a 10% drop out rate included, this would result in a total of 40 compliant patients.

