8.2 Statistical analysis plan

8.2.1 Primary analysis

The IPSS score change at 6-week from baseline will be calculated with 95% confidence interval and compared between two experiment groups through Mann-Whitney test. The baseline, minimum three treatment period IPSS scores, and the 10-week biopsy IPSS scores are required in order for the patient to be evaluable.

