8.2.2 Secondary analysis

- a) For the secondary end point of recurrence rate defined by 10-week biopsy, the Chi-squares test is used to test the rate difference between the two arms, and a logistic regression is needed to further adjust potential covariates, e.g. total BCG therapy dose.
- b) For the secondary end point of the total dose of intravesical therapy administered over 6 weeks, we consider the two-sample t test and/or sum rank test to test the difference between two arms. If genistein supplement works by reducing symptoms and maintaining the therapy dose, we expect to see a higher total therapy dose in its arm than in the placebo arm.
- c) We will also explore the change of IPSS score over time by the GEE model in which the repeated measurements of IPSS score are treated as outcome. Treatment, time, interaction between treatment and time, and intravesical therapy dose enter the model as predictors and time-dependent covariate.

9. Adverse Event Reporting:

According to 21 CFR 312.32, *Adverse event* means any untoward medical occurrence associated with the use of a drug in humans, whether or not considered drug related. A *Serious adverse event* or *serious suspected adverse reaction* is an adverse event or suspected adverse reaction is considered "serious" if, in the view of either the

investigator or sponsor, it results in any of the following outcomes: Death, a life-threatening adverse event, inpatient hospitalization or prolongation of existing hospitalization, a persistent or significant incapacity or substantial disruption of the ability to conduct normal life functions, or a congenital anomaly/birth defect. Important medical events that may not result in death, be life-threatening, or require hospitalization may be considered serious when, based upon appropriate medical judgment, they may jeopardize the patient or subject and may require medical or surgical intervention to prevent one of the outcomes listed in this definition. Examples of such medical events include allergic bronchospasm requiring intensive treatment in an emergency room or at home, blood dyscrasias or convulsions that do not result in inpatient hospitalization, or the development of drug dependency or drug abuse.

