Adverse events will be recorded at each study visit via direct patient communication as well as through patient questionnaires. The severity of the AEs will be graded according to NCI CTCAE Version 4.0. Subjects with toxicities of Grade 3 or higher will be immediately discontinued from the study pill for the remainder of treatment. Any BCG intravesical therapy modifications will be done according to doctor analysis with an effort on alleviating toxicities as needed. In order to be evaluable, patients will need to receive at least three BCG instillations. If BCG treatment is interrupted or discontinued, only IPSS scores will be obtained via phone call. If a SAE occurs, we will promptly report it to our IRB upon discovery and follow the subject until the SAE is resolved. Adverse events will be reported to the IRB according to their requirements.

IND safety reports will be sent to the FDA in accordance with 312.32 the FDA's *Guidance for Industry and Investigators: Safety Reporting Requirements for INDs and BA/BE studies*. IND safety reports will document any aggregate adverse events, adverse reactions suspected adverse reactions, or serious adverse events. If the event is considered to be unexpected fatal or life-threatening, the IND safety report will be sent as soon as possible and within 7 business days of the investigator being notified. If necessary, the investigator will report any serious or life-threatening event initially by facsimile or telephone prior to formal submission. IND safety reports will also be submitted to the FDA if any related safety information is released from other sources. Any nonserious adverse events will be reported to the FDA in aggregate on an annual basis.

10. Data and Safety Monitoring Plan (DSMP):

Once the study has reached 50% accrual, investigators will plan to initially evaluate the results. A group of physicians from the Winship Cancer Institute at Emory University will review the data and questionnaires to see how patients are reacting to the genistein supplement arm or whether there are drug compliance issues, such as failure to take the pills per protocol. If the genistein supplement arm has statistically significant toxicities reported or greater degree of bladder cancer biopsies then we will immediately

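### The three-instillation evaluability rule in Section 9 is not kept away from the total BCG dose endpoint, whose analysis population is unstated; applied as written, it selects on part of that outcome

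*Combined protocol and SAP*

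**What the plan says.** The dose endpoint is set in Section 4.2(b): "A second secondary study endpoint will be the total dose of intravesical therapy administered over the 6 weeks of treatment". That section frames the question as whether dosing needs to be cut less on genistein, looked at week by week. Section 8.2.2(b) gives the test, "we consider the two-sample t test and/or sum rank test to test the difference between two arms", and the expected direction: "we expect to see a higher total therapy dose in its arm than in the placebo arm". It states no analysis population.

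There are two evaluability statements, and they differ:

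- Section 9 (Adverse Event Reporting): "In order to be evaluable, patients will need to receive at least three BCG instillations".
- Section 8.2.1 (Primary analysis): "The baseline, minimum three treatment period IPSS scores, and the 10-week biopsy IPSS scores are required in order for the patient to be evaluable".

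The first is a condition on BCG received; the second is a condition on questionnaires only. No intention-to-treat or all-randomised set is defined anywhere. Section 9 also says what happens once BCG stops: "If BCG treatment is interrupted or discontinued, only IPSS scores will be obtained via phone call".

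**The concern.** The number of instillations received is a main component of total dose and becomes known only after randomisation. Requiring at least three of them before a patient counts, and then comparing total dose, conditions the comparison on part of its own result. A patient who gives up BCG after one or two instillations because of symptoms is the kind of patient the dose endpoint should register, and the rule as written would take that patient out.

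Such patients are possible under the plan. Section 2 says symptoms can begin with the first instillation, and both the visit table in Section 5 and Section 9 provide for BCG being interrupted or discontinued. If genistein does lower the symptom burden, early stopping would plausibly be more common on placebo. The exclusions would then be unequal, the analysed groups would no longer be the randomised groups, and the dose difference would be understated.

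**Working it through.** **The plan's own figure.** The plan gives no power or effect size for the dose endpoint. Its only power figure is 83% for the primary IPSS comparison (20 per arm, difference 6 − 3 = 3, SD 3.5, one-sided 0.05, Mann-Whitney). With the Mann-Whitney efficiency 3/π, the effective n is 20 × 3/π = 19.1 per arm, the noncentrality is 3 / (3.5 × √(2/19.1)) = 2.65, and the noncentral t power is 83.0%. The figure reproduces, but it says nothing about dose.

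**Which patients the rules treat differently.** A patient who stops after two instillations and answers the IPSS by phone can meet Section 8.2.1 (baseline, three treatment-period scores, 10-week score) and still fail Section 9. The instillations given to that patient are a definite number, and each one not given adds zero to the total, so the endpoint is defined for that patient.

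**The rule counts instillations, not dose.** Section 2 says "Dose reduction is generally done in 50% increments". Three half doses total 3 × 0.5 = 1.5 full-dose equivalents and stay in; two full doses total 2.0 and are removed. The rule therefore removes many of the lowest-dose patients, but not exactly those.

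**Illustration 1: means.** All rates and means here are assumptions. Early stoppers receive 2 full doses; the rest average 5.0 (placebo) and 5.2 (genistein). The mean in an arm with stopping proportion p is 2p + (1 − p)m. The evaluable difference is always 5.2 − 5.0 = 0.20.

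| Early stopping, placebo v genistein | Placebo mean | Genistein mean | Difference, all randomised | Difference, evaluable |
|---|---|---|---|---|
| 5% v 5% | 0.10 + 4.75 = 4.85 | 0.10 + 4.94 = 5.04 | 0.19 | 0.20 |
| 10% v 5% | 0.20 + 4.50 = 4.70 | 5.04 | 0.34 | 0.20 |
| 15% v 5% | 0.30 + 4.25 = 4.55 | 5.04 | 0.49 | 0.20 |
| 20% v 5% | 0.40 + 4.00 = 4.40 | 5.04 | 0.64 | 0.20 |

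At 15% v 5% the share lost is (0.49 − 0.20)/0.49, about 60%. With equal stopping almost nothing changes.

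**Illustration 2: simulation.** 22 per arm, 5,000 runs, two-sided t test at 0.05. Early stoppers receive one or two full doses. The others receive six instillations, and a stated share of them are halved after two to five full doses. All rates are assumed.

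| Early stopping | Share halved among the others | Difference, all v evaluable | Power, all v evaluable |
|---|---|---|---|
| 0% v 0% | 30% v 15% | 0.19 v 0.19 | 18% v 18% |
| 5% v 5% | 30% v 15% | 0.18 v 0.19 | 10% v 19% |
| 15% v 5% | 30% v 15% | 0.59 v 0.19 | 30% v 19% |
| 20% v 5% | 30% v 15% | 0.79 v 0.19 | 42% v 17% |
| 15% v 5% | 20% v 20% | 0.43 v 0.01 | 16% v 5% |
| 20% v 5% | 20% v 20% | 0.64 v 0.00 | 27% v 5% |

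Where the arms differ only in early stopping (last two rows), the rule removes the whole difference.

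**Rank-sum check.** With the means of illustration 1, 22 per arm and an assumed spread of 3 to 6 doses among the others, two-sided rank-sum power is about 20% in all randomised v 10% in evaluable patients at 15% v 5%, and about 9% v 10% at 10% v 10%.

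**The case against.** The best defence is that the dose analysis may never have been meant to use evaluable patients only. Section 8.2.2(b) does not say so, the SAP's own evaluability sentence sits under the primary analysis and concerns questionnaires, and the Section 9 sentence comes directly before the one on collecting IPSS by phone. It can be read as a rule for the IPSS analysis. This stands in part: a reader might infer that early stoppers are definitely dropped from the dose comparison, and the documents do not establish that. But the sentence carries no limit and no other population is defined, so an analyst following the text could apply it, and could choose after seeing the data.

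The expected response to symptoms in Section 2 is dose reduction, not stopping. A patient halved from week 1 who keeps attending stays in the comparison. This also stands: 4.2(b) is not simply a count of instillations, and excess early stopping on placebo is an inference from the hypothesis, not something the plan states.

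With equal early stopping, bias is negligible and including everyone can cost t-test power (10% v 19% at 5% v 5%). That is correct. The rank-sum test, already named in the plan, loses little (about 9% v 10% at 10% v 10%). The comparison has low power either way, so the reason for the change is validity, not a power gain.

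Finally, the loss is only toward no difference. That is true for the hypothesised direction. If early stopping were reversed, at 5% placebo v 15% genistein, illustration 1 gives (0.30 + 0.85 × 5.2) − 4.85 = 4.72 − 4.85 = −0.13 in all randomised patients against +0.20 in evaluable patients, and the rule would favour genistein.

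**Conclusion.** The concern holds in limited form. Section 9 sets an unqualified evaluability rule on BCG received, Section 8.2.2(b) names no population for total BCG dose, and no all-randomised set exists. Applied as written, the rule selects on a post-randomisation component of the endpoint. It biases the dose difference toward zero if early stopping is more common on placebo, and does little or nothing if stopping is equal or absent.

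The size cannot be derived from the documents, which give neither an early-stopping rate nor a dose SD. The 0.49 v 0.20 example rests wholly on the assumed 15% v 5% stopping after two instillations and on means of 5.0 v 5.2 in the rest. Two stronger readings are not supported: that the plan explicitly excludes these patients from the dose test, and that the rule removes exactly the patients with the lowest dose.

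Separately, and without any assumption, the evaluability statements in Sections 8.2.1 and 9 differ and need reconciling. The endpoint is secondary, so this should be corrected but does not threaten the primary comparison's stated power.

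**What to change.** 1. In Section 8.2.2(b), state that total BCG dose is compared in all randomised patients as assigned, that each instillation not given contributes zero, and that the test is the rank-sum test already named there.
2. In Section 9, state that the three-instillation rule does not apply to objective 4.2(b).
3. Reconcile the evaluability statements in Sections 8.2.1 and 9, saying for each endpoint which patients are analysed.

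The cost is a few sentences and no new assessments, since 4.2(b) already calls for dose by treatment week. There are two downsides. Stops unrelated to symptoms also count as low dose and add some noise. Dose records must also be kept for patients who drop out; the documents do not say whether they are, and Section 8.1 expects 10% drop-out or non-compliance. The change concerns the analysis population only; no BCG dosing rule is altered.
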